Study Title	Stanford Tobacco Treatment Services – Virtual Reality Treatment for Smoking Cessation
Study Description	Testing feasibility of a virtual reality app for smoking cessation among 20 patients, from the Stanford Cancer Center, who smoke cigarettes daily as part of the Tobacco Treatment Services.
Study Purpose (for ClinicalTrials.gov)	Health Services Research
Secondary Objective(s)	Quit status and attempt to quit. Learning whether those who also opted in for tobacco treatment services (e.g. NRT, counseling sessions) have different outcome than the ones who used the MindCotine app only
Secondary Endpoint(s)	End of treatment assessment quit status, making a quit attempt during the past 6 weeks, use of cessation medications, smoking reduction (EOT cigarettes per day compared to cigarettes per day at baseline), MindCotine usage, dropout, and adverse events.
Eligibility Criteria	Daily or some day cigarette smokers (>9 cigarettes/week), English or Spanish fluent, has compatible smartphone, willing to interact with the app for 6 weeks, willing to complete survey assessments, no hx of seizures
Treatment and Procedural Summary	Participants are recruited during outreach as part of the Tobacco Treatment Services. The study is proposed as a treatment option. If interested, potential participants will complete a phone screen, and if still interested, proceed to the study consent form. After the study consent form is signed, VR kit with the app code for access to the full MindCotine virtual reality program will be mailed to the participant. The participant will start treatment, engage in treatment for 6 weeks and complete the end of treatment questionnaire. The participant can utilize the app for up to a year if they wish to. All participant data on the app will be deleted after that year has passed. Data will be analyzed. A summary of analyses will be provided to MindCotine. The team will decide whether to invest in MindCotine as a treatment option for patients.

Considerations

Collection, the statistical plan is descriptive in nature. Descriptive statistics (e.g., means/SD, frequencies, ranges) will summarize participant demographic and tobacco use characteristics, changes in tobacco use over time, MindCotine app usage, feedback on the MindCotine program, dropout, and any adverse effects. Factors that indicate feasibility will include (i) interest among our patient population in using the app, which will be offered at no cost; (ii) among those patients who are interested, that they are able to onboard and make use of the app; and (iii) patient ratings of recommending the app to others. Feasibility metrics would be at least (i) 80% interested in using the app; (ii) 75% of interested patients onboarded and using the app; and (iii) 70% recommending the app to others. Efficacy goals will be examining tobacco use reduction and quitting with goals of at least (iv) 50% reducing tobacco use and 10% quitting. Additionally, the quit rate among participants in this pilot will be compared to the quit rate

Study Duration

Estimated study period is 9 months to recruit, complete assessments with 100 patients, and data analyses. After the initial outreach and consent, the participant will receive their VR kit in 3-5 business days, start the intervention, and have a final survey after the 6-week period. Data analyses

Subject Duration

The study duration is 6 weeks or 1.5 months for participants from baseline to end of study.

LIST OF ABBREVIATIONS & TERMS

pp	le application	NCI	National Cancer Institute
LIA	onal Laboratory Improvement endments; Certification	On-study date	Defined (per OnCore) as date of subject’s first research-related procedure, scan, or treatment
R	lete response	PR	Partial response
SMP	Safety Monitoring Plan	SCI	Stanford Cancer Institute
DAAA	and Drug Administration endments Act	SOP	Standard Operating Procedures
UI	for Guidances under Stanford search Compliance Office	TTS	Tobacco Treatment Services
CMJE	Committee of Med Journal Edito	UP	Unanticipated Problem

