2.1.4. Scientific Justification for Study Design

This study is a pilot to test feasibility of the app among patients from the Stanford Cancer Center who smoke cigarettes daily. There will be 20 kits available for testing feasibility. Outcomes will be assessed pre-intervention and post-intervention.

Factors that indicate feasibility will include (i) interest among our patient population in using the app, which will be offered at no cost; (ii) among those patients who are interested, that they are able to onboard and make use of the app; and (iii) patient ratings of recommending the app to others. Feasibility metrics would be at least (i) 20% interested in using the app; (ii) 75% of interested patients onboarded and using the app; and (iii) 70% recommending the app to others. Efficacy goals will be examining tobacco use reduction and quitting with goals of at least (iv) 50% reducing tobacco use and 10% quitting. Not feasible would be indicated by **less than** (i) 20% interested in using the app; (ii) 75% of interested patients onboarded and using the app; and (iii) 70% recommending the app to others.

Given the novelty of the program (virtual reality app) and our older patient population, we are interested in seeing do patients have interest in using the program, are they able to onboard at a distance (from home), do they make use of the app, and would they recommend the app to others. We also will examine whether they reduce or quit their tobacco use. If the metrics above are met, we would consider adding MindCotine to the choices available.

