10. STATISTICAL CONSIDERATIONS

A pilot study (n=20), with short-term outcomes, and limited data collection, the statistical plan is descriptive in nature. Feasibility metrics would be at least (i) 20% interested in using the app; (ii) 75% of interested patients onboarded and using the app; and (iii) 70% recommending the app to others. Efficacy goals will be examining tobacco use reduction and quitting with goals of at least (iv) 50% reducing tobacco use and 10% quitting. Descriptive statistics (e.g., means/SD, frequencies, ranges) will summarize participant demographic and tobacco use characteristics, changes in tobacco use over time, MindCotine app usage, feedback on the MindCotine program, dropout and any adverse effects. The quit rate among participants in this pilot will be compared to the quit rate for our tobacco treatment service as a clinical benchmark.

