10.1.2. Sample Size Determination

This is a pilot study to see if MindCotine is feasible for patients from the Stanford Cancer Center who smoke. MindCotine will be providing 20 VR kits for free for this purpose. The sample size is N=20. We view a sample size of 20 as sufficient to gain an initial understanding of interest in the program and use of the program in our patient population.

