10.2.1. Primary Endpoint

App feasibility and acceptability – that is, interest in using the app, onboarding to the app, and recommending the app to others.

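### The pass mark for interest, the first primary feasibility metric, is 80% in the synopsis and 20% in the body, so any total of 25 to 96 patients invited passes one and fails the other.

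*Combined protocol and SAP*

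**What the plan says.** Section 10.2.1 defines the primary endpoint as feasibility and acceptability: "interest in using the app, onboarding to the app, and recommending the app to others". Each component has a pass mark.

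- **Protocol Synopsis, statistical considerations:** "Feasibility metrics would be at least (i) 80% interested in using the app".
- **Sections 10 and 10.2:** "Feasibility metrics would be at least (i) 20% interested in using the app".
- **Section 2.1.4:** the same 20% criterion, followed by the converse rule, "Not feasible would be indicated by less than (i) 20% interested in using the app".

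Section 2.1.4 then links the marks to the decision: "If the metrics above are met, we would consider adding MindCotine to the choices available".

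The other marks (75% onboarded, 70% recommending, 50% reducing, 10% quitting) are the same in the synopsis and the body.

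The synopsis entry on study duration also speaks of a period to "complete assessments with 100 patients, and data analyses". Section 10.1.2 says "The sample size is N=20", and Section 3.4.2 closes enrollment at 20 signed consents.

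**The concern.** Two values are in force for one primary criterion. The plan is descriptive, with no hypothesis test, so these marks are its only formal standard for calling the app feasible. They also bear on what follows: Section 2.1.4 makes adding the app to the service depend on them, and Section 10.5.4.3 makes a larger efficacy evaluation depend on feasibility.

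The number consenting is fixed in advance at 20, so the interest result depends only on how many patients are invited. Once that number is known, a reader could cite whichever mark gives the preferred answer and point to approved protocol text for it. The gap between 20% and 80% is wide enough to contain most plausible results.

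**Working it through.** Neither threshold is derived from other inputs, so there is no calculation of the plan's to reproduce. The check is which results satisfy each mark.

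**Inputs**
- Thresholds: 80% (synopsis); 20% (Sections 2.1.4, 10, 10.2).
- Estimator (Sections 10.2.1.1, 10.4, 10.4.2): interest = 19/(N − 1), where N is the number of patients presented with the study on outreach calls.
- Stopping point (Section 3.4.2): 20 signed consents.
- Context (Section 3.4.2): 34% of patients reached engage in treatment.

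**Step 1. Largest N that meets each mark**
- 80%: 19/(N − 1) ≥ 0.80 gives N − 1 ≤ 23.75, so N ≤ 24. Check: 19/23 = 0.826; N = 25 gives 19/24 = 0.792.
- 20%: 19/(N − 1) ≥ 0.20 gives N − 1 ≤ 95, so N ≤ 96. Check: 19/95 = 0.200; N = 97 gives 19/96 = 0.198.

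| Patients invited | Synopsis (80%) | Body (20%) |
|---|---|---|
| 24 or fewer | met | met |
| 25 to 96 | not met | met |
| 97 or more | not met | not met |

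The conflict does not depend on the choice of estimator. With the simple ratio 20/N, the limits are N ≤ 25 and N ≤ 100.

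**Step 2. How often the marks would disagree (illustration)**

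Assume each invited patient consents independently with probability p and decides before the next is invited. Enrollment stops at the 20th consent, so P(N ≤ 24) = P(Bin(24, p) ≥ 20) and P(N ≤ 96) = P(Bin(96, p) ≥ 20). The probability of disagreement is the difference.

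| Assumed p | Meets 20% mark | Meets 80% mark | Marks disagree |
|---|---|---|---|
| 0.20 | 0.459 | <0.0001 | 0.459 |
| 0.25 | 0.856 | <0.0001 | 0.856 |
| 0.34 | 0.998 | <0.0001 | 0.998 |
| 0.50 | >0.999 | 0.0008 | 0.999 |
| 0.70 | 1.000 | 0.111 | 0.889 |
| 0.80 | 1.000 | 0.460 | 0.540 |
| 0.90 | 1.000 | 0.915 | 0.085 |

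**Step 3. The 100 patients**

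Read as the number assessed, 100 contradicts the 20 kits and 20 consents. Read as the number invited, it gives 19/99 = 0.192 under the plan's formula, just below the 20% mark.

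**The case against.** The strongest reply is that the synopsis was simply not updated. The body gives 20% four times (twice in Section 2.1.4, once each in Sections 10 and 10.2). The only explicit not-feasible rule is in Section 2.1.4, at 20%, beside the sentence on adoption. The synopsis states a target and no converse rule. On that reading there is one complete decision rule and one stray figure, and picking the mark afterwards would be harder than it first appears. This is the likeliest explanation, but it is an inference: the documents have no rule that the body overrides the synopsis, and the protocol history in Section 12 does not mention the threshold.

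Other points stand as limits:
- The marks agree at 24 or fewer invited and at 97 or more, so the conflict is not universal. At a true interest of 20%, both are missed about 54% of the time (1 − 0.459).
- The 34% is engagement in the service's treatment, and Section 3.4.2 says interest in the app is unknown. That section also lets patients take time to decide, so some may be undecided when the 20th consent is signed. The probabilities are therefore illustrative.
- The language is soft. The team would only consider adding the app, interest is one of three metrics, and participants are not affected.
- The 100-patient figure is a separate inconsistency that does not alter the threshold conflict.

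None of this removes the contradiction between the two current texts.

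**Conclusion.** The concern holds and must be fixed. One component of the primary endpoint has two pass marks, 80% and 20%. Under the plan's own formula they give different answers for every total from 25 to 96 patients invited. That range assumes exactly 20 consents and the 19/(N − 1) estimator.

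For assumed true interest between 25% and 70%, the marks would disagree with probability at least 0.86. The conflict itself needs no probability assumption.

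**What to change.** State one threshold in all five statements: the synopsis, both sentences of Section 2.1.4, Section 10 and Section 10.2. If 20% is intended, as the body suggests, only the synopsis figure changes. If another value is intended, the not-feasible sentence in Section 2.1.4 must change with the rest. Beside the threshold, give the equivalent count (at 20%, no more than 96 patients invited for 20 consents), and note that it must be restated if accrual stops short, which Section 5.11 allows for.

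In the same edit, change the synopsis's 100 patients to 20. If 100 is meant as the number invited, say so and check it against the chosen threshold.

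The cost is two figures in the synopsis if 20% is kept, plus a clarifying phrase. It needs no new data and no extra patients, and should be done before the number invited is known.

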1. INTRODUCTION

1.1. Study Rationale

There are patients from the Stanford Cancer Center who use tobacco and have difficulty reducing their use or quitting. Tobacco use exacerbates health conditions and hinders treatment. Currently, Tobacco Treatment Services include nicotine replacement therapy, cessation medication consultations, individual counseling sessions, group counseling sessions, and referrals to the quit line. Some patients have exhausted their options in smoking cessation. The MindCotine virtual reality smoking cessation app is a novel approach to tobacco cessation, and is an option to consider adding as part of the tobacco treatment service.

1.2. Background

1.2.1. Overview of study intervention

Patients who use tobacco are identified from Stanford Cancer Clinics, and our Tobacco Treatment Specialist reaches out to them to engage in tobacco cessation. If a patient is interested in the VR treatment option, patients will be checked on whether they would be able to use the VR intervention (e.g. smokes, smartphone compatibility, language fluency), and then is sent the intervention kit. Patients will be followed up with post intervention to check on effectiveness of the treatment. Participation in the 6-week VR intervention is voluntary and will not affect access to other tobacco treatment options. Treatment outcomes will be analyzed with pre/post survey data and app use frequency data.

Data obtained from the 20 patients trying out this intervention will inform whether MindCotine is a worthwhile treatment option to offer. If MindCotine proves to be effective among our patients, we may have another treatment option for our patients, especially for those who have exhausted their smoking cessation options.

MindCotine is the first virtual reality intervention for smoking cessation with pilot results supporting remote and self administration feasibility. Abstinence rates in their pilot study had similar results to other studies with smoking cessation apps.

(<http://www.jmir.org/2020/7/e17571/>)

In the pilot study, the average age of the participants was 41, supporting that the users do not necessarily have to be tech savvy. This suggests that MindCotine may be an effective digital health intervention for our patients, who tend to be older.

1.2.2. Mechanism(s) of Action for Stanford Tobacco Treatment Services – Virtual Reality Treatment for Smoking Cessation

The MindCotine 6-week training period consists of a playlist of audiovisual content (2D, audio, Virtual Reality) lasting from 2 to 10 minutes each, and a series of CBT-based self-reflective questions. The participant can select their Quit-Date at any given time, and will receive notifications accordingly. The 2D and audio activities are based on formal mindfulness exercises

based on breathing techniques, body scan, recognition of thoughts, emotions, and the impulse of smoking.

The VR therapy exercises include the following topics:

1. The Act of Smoking
2. RAIN meditation
3. Stress at work
4. Bodily sensations
5. Deep emotions
6. Nicotine anonymous
7. Alcohol as a trigger

Each content consists of a 2-minute animated environment to induce meditative states of mind, 6 minute of exposure with real people, and 2 more minutes of animated environment to again, induce a meditative mindset.

1.2.3. Clinical Experience

MindCotine is the first virtual reality intervention for smoking cessation with pilot results supporting remote and self administration feasibility. This pilot studied 120 participants from Buenos Aires, Argentina (mean age 43.2 years, SD 9.50; 47.5% female). Abstinence rates in their pilot study had similar results to other studies with smoking cessation apps. Follow up rates were >90% for both the treatment and control groups. At postintervention, the treatment group reported 23% abstinence compared with 5% of those in the control group ($\chi^2 = 8.3$; $P = .004$).

In the pilot study, the average age of the participants was 41, supporting that the users do not necessarily have to be tech savvy. This suggests that MindCotine may be an effective digital health intervention for our patients, who tend to be older. Long term outcomes have not been studied.

The manuscript of the pilot trial can be found on (<http://www.jmir.org/2020/7/e17571/>).

Our Tobacco Treatment Services has grown, and we are exploring novel treatments that incorporate technology for scalability. A manuscript of the project's progress is available at <https://doi.org/10.3390/ijerph17062101>

1.2.4. Importance of the Clinical Trial

The purpose of the Tobacco Treatment Service is to expand access to and engagement in tobacco cessation treatment services at the Stanford Cancer Center to patients and their family members. The project utilizes technological innovations to deliver provider education; optimize chart documentation, referral, and team communications; and extend treatment service delivery. Adding VR treatment is an option we are considering for patients who would like to quit smoking.

For patients with cancer and use tobacco, helping them quit can: Reduce treatment side effects (e.g. from surgery, radiation, and/or chemotherapy); Increase the effectiveness of treatment; Decrease the risk of cancer recurrence or of the development of other types of cancers; and improve overall well-being and quality of life.

1.3. Potential Risks and Benefits

1.3.1. Known Potential Risks of MindCotine

The virtual reality simulation could potentially trigger seizures. Those with a history of epilepsy should not use this treatment option.

There is also the possibility of side effects from the virtual reality simulation. Symptoms may include dizziness, disorientation, nausea, sweating, or headaches.

1.3.2. Known Potential Risks of Study Procedures

Given that the pilot study aims to see feasibility of VR program in reducing tobacco smoking, we do not envisage that participation in the study will be associated with elevated risk. We are not assessing suicidal ideation in our questionnaires. Some risk is always present in studies that involve human participants. Such risk may include the following:

1. Data Protection and Privacy: All study data are gathered on a HIPAA compliant web platform that resides behind Stanford security firewalls and has been tried and tested by the University for several years, thus actual risk from data breach for study data is low. All assessments, including the screening utilizing HIPAA compliant survey administration tool commonly used by Stanford University in its clinical trials (Qualtrics or REDCap). Given the high data protection safeguards embedded within Qualtrics or REDCap, there is little risk to the subject associated in regards to their privacy and/or confidentiality.

Research material obtained from human subjects will involve behavioral and psychological assessments including self-report questionnaires. All data will be obtained specifically for purposes of this pilot study. Data that are obtained from the Qualtrics/REDCap surveys will be stored and protected within Qualtrics/REDCap.

Data that are obtained via MindCotine: MindCotine established a connection app-server with secure layer; Data are encrypted while traveling the Internet. MindCotine have servers within the Google infrastructure with the highest standards of security and privacy. Emails will be asked for during app registration. IP addresses will be temporarily collected for Firebase (part of the app infrastructure) to work. All participant data on the app will be deleted a year after starting the app.

Only members of the research team (PI, post-doc, research assistant) will have access to the data. The clinical and research teams will have access to PHI, as described with IRB 48420. MindCotine requires emails for user registration with their app. Otherwise, no PHI is required.

Data sharing: Data shared between MindCotine and Stanford will be conducted using Stanford Medicine Box and secure email. MindCotine will share user data with the Stanford team. After the data are merged by the Stanford team, identifiers will be removed and each row of participant data will be assigned a number from 001-020. The Stanford team will analyze the data and provide a summary of outcomes (overall demographics, overall engagement with tobacco treatment interventions opted into at initial outreach, cessation outcomes) to MindCotine. The summary of outcomes will not have any identifiable information, and will describe the pilot sample.

2. Potential Upset due to Survey Questions: Foreseeable risks to subjects include the possibility that some assessment questions and/or treatment procedures may be upsetting to subjects. Experience at Stanford with similar populations has indicated that the risk of emotional upset during the assessments is low and if it occurred, the upset would likely not be serious in nature and temporary. Such risks will be minimized by asking a small amount of questions for tobacco use assessment, compatibility with the program satisfaction with program, and likelihood of recommending the program. Potential participants will also be informed that they may drop out of the study at any time and if requested, appropriate treatment referrals would then be given.

3. Risk of treatment avoidance due to engagement with the intervention. No treatment is being withheld. The pilot study offers the VR program to 20 participants as an option of the Tobacco Treatment Service, allowing for participants to also engage in other tobacco cessation treatment.

1.3.3. Known Potential Benefits

May help patients reduce smoking or help them quit.

2. STUDY DESIGN, OBJECTIVES, AND OUTCOMES

2.1. Study Design

2.1.1. Overall Design

The intervention model of this study is **Single Group**.

2.1.2. Primary Purpose of the Study

Health Services Research: To test feasibility of the MindCotine virtual reality program for smoking cessation among 20 patients. After the pilot, the team will decide whether to invest in MindCotine as a treatment option to offer to patients.

